5.2 Recruitment Methods

Sample Size

Providers: Up to 100 providers will be enrolled for Aims 1 and 2, and all intervention arm providers (up to approximately 38) will be invited to complete the qualitative interview at the end of the patient recruitment/enrollment phase.

Patients: no more than 570 patients will be enrolled for the RCT, and up to 30 intervention-arm patients will complete the qualitative interview after the post-visit survey.

Clinic Leaders: Up to 35 clinic leaders will complete qualitative interviews at the end of the patient recruitment/enrollment phase.

Identifying and Recruiting Study Participants

Providers: Providers from each study site will be identified as potentially eligible for study recruitment using data available through CDW. These data will be accessed by our data requisitioner using the VA Informatics and Computing Infrastructure (VINCI). Recruitment emails will be sent to potentially eligible providers by study staff (see attached email, Attachment F). Recruitment emails will include a study information statement for providers (Attachment G) and will instruct providers to respond if they do not wish to be contacted about participation in the study. Opt-out responses from providers will be collated by the study manager. Recruitment lists will be made available to study RAs at least one week later. RAs will contact providers by telephone, email, and MS Teams messenger. Screening, consent, and study enrollment will occur over the telephone (see attached script, Attachment H). No more than 3 voice messages, 3 emails, and 3 MS Teams direct/instant messages will be sent by study staff to potentially eligible providers that have not opted-out of study contact.

Patients: After study providers have been enrolled, the data requisitioner will pull lists of all potentially eligible VA patients (women ages 18-44 without medical record evidence of infertility) empaneled to enrolled providers. Recruitment letters will be mailed to these patients (Attachment I) by the study manager or research coordinator at the start of the study.

Recruitment letters will include a study information statement for patients (Attachment J) and a postage-paid opt-out postcard (Attachment K) which patients may return by mail if they do not wish to be contacted further about study participation. The data requisitioner will pull lists of potentially eligible patients assigned to enrolled provider primary care panels again at 6 and 12 months into the patient recruitment phase and recruitment letters will be mailed to any new patients (those not previously mailed a recruitment letter). The study manager and research coordinator will track any opt-out postcards in the patient crosswalk database so that no further contact will be made with those patients.

During the active patient recruitment phase of the study, the data requisitioner will pull weekly lists of potentially eligible VA patients (same criteria as above) that are scheduled to see enrolled study providers during the following week. In-person, telephone, and video-conferencing appointments will be eligible study visits. The study manager, research coordinator, or database manager will match these lists against the patient crosswalk database to remove any patients to whom a recruitment letter was never sent, who returned the opt-out postcard, who already enrolled in the study, or who have declined participation or withdrawn from the study previously.

Those vetted recruitment lists will be distributed to the study RAs, who will make contact with patients prior to their appointments by email (for screening, when email addresses are available) and subsequently by telephone (for screening, consent and enrollment; see attached script, Attachment L).

- **Email recruitment:** To provide Veterans a second opportunity to opt-out of the study, RAs will send an unencrypted email from a designated study email account (to which only study staff have access). The recruitment email will introduce Veterans to the study and invite them to complete a confidential online questionnaire (using the Qualtrics online survey program) as a means of opting-in or opting-out of being contacted about the study and screening for eligibility. The study information statement (which was previously mailed to all potentially eligible participants; Attachment J) will also be made available as a downloadable document within the online Qualtrics recruitment survey. The recruitment email does not contain the Veteran's name or other PII, and contains no statements that could be used to infer anything about the Veteran's health status. This strategy of recruiting Veterans by email is Veteran-centered because it allows Veterans who may have received the mailing many months ago, and who may have forgotten details or changed their mind about the study in the intervening time, to reconsider whether they are interested in the study and let us know before receiving recruitment calls.
- **Telephone recruitment:** If we fail to receive an opt-out (by mail, Qualtrics survey, or telephone) from a Veteran at 7 days from the Veteran's appointment date, we will contact the Veteran by telephone to invite them to learn more about the study and consider participating.

Study RAs will be responsible for recruiting, consenting and collecting data from patients at all study sites. To avoid overlap, RAs will be assigned specific shifts when they will be responsible for conducting recruitment calls/emails, and survey phone calls. RAs will document contact attempts and call outcomes in a shared recruitment list (stored on a secure VA server) to avoid overlap and ensure recruitment is synchronized. Additionally, the Study Manager and/or Study Coordinator will provide daily oversight and coordination to ensure accuracy.

Clinic Leaders: Potentially eligible clinic leaders will be identified by study co-investigators at engaged study sites and site contacts at non-engaged study sites. Recruitment emails will be sent to potentially eligible clinic leaders by the study team (see attached email, Attachment M). Recruitment emails will include a study information statement for clinic leaders (Attachment N) and will instruct clinic leaders to respond if they do not wish to be contacted about participation in the study. Opt-out responses will be collated by the study manager. Study staff conducting qualitative interviews will contact clinic leaders up to 3 times by telephone, 3 times by email, and 3 times by MS Teams instant/direct message for recruitment purposes. Screening, consent, and enrollment will happen over the telephone (see attached script, Attachment O).

Payment

Providers and Clinic Leaders: VA employees will not receive payment for participation in the study.

Patients: Enrolled patients will receive \$25 by electronic funds transfer from VA or receive a \$25 Amazon gift card after completing three of the study surveys (baseline, at 3 months, and at 6 months), and, when applicable, after completing a qualitative interview. Enrolled patients who complete the post-visit survey after their scheduled primary care appointment will receive \$50 by electronic funds transfer from VA or a \$50 Amazon gift card. This means that patients can receive up to \$125 for completing all study surveys for Aims 1 and 2, and an additional \$25 if invited to do a qualitative interview for Aim 3. Payments will be initiated after each completed study survey or interview; thus, patients will be paid for partial study participation. We will give Veterans the option of receiving a gift card or an electronic fund transfer from VA as payment for their study participation. VA electronic fund transfer payments are distributed through the VA Austin payment center. If a Veteran would like to receive their payment by electronic funds transfer and they have not previously filled out VA Form 10-091, Veterans have the option to complete a paper VA Form 10-091 (returned by mail) or complete VA Form 10-091 online through the VA's online Customer Engagement Portal. If a Veteran chooses to receive their payment as an Amazon gift card, these will be mailed by the study team or sent as a gift card claim code in an unencrypted email from the study email account. No Veteran identifiers would be included in the email (Attachment Z). Veterans may experience a delay in receiving electronic funds transfer payments for up to 6 months due to processing time.

5.3 Informed Consent Procedures

Study Staff Involved in Screening, Consent, and Enrollment:

Screening, verbal consent, and enrollment of providers and patients will be conducted by study RAs following the attached scripts (Attachments H and L). Study staff who will conduct qualitative interviews (investigators, study manager, or research coordinator) will conduct screening, verbal consent, and enrollment with clinic leaders before the qualitative interview following the attached script (Attachment O). The PI/SC will be responsible for ensuring that all study staff are up-to-date on VA-required human subjects protection trainings. The PI/SC and study manager will provide further specific training on obtaining verbal consent during a study orientation that will be provided to RAs, which will include role playing verbal consent scenarios.

Waiver of Documentation of Consent for Entire Study:

Because the study poses minimal risk to participants, and because recruitment and enrollment would not be feasible in-person for all participants, we are requesting a waiver of documentation of consent for the entire study. Verbal consent procedures will be conducted over the telephone by study staff after recruitment emails or physical letters with opt-out option are sent to potentially eligible participants.

Study staff obtaining verbal consent will be trained in consent processes, including to understand the importance of consent processes being interactive and non-coercive. Study staff obtaining verbal consent will be trained not to continue with the consent and enrollment if they have any reason to believe that a potentially eligible participant is not able to provide informed consent at the time of the telephone call.

Alteration of Consent During Patient Enrollment:

We are asking for an alteration of consent processes during patient enrollment, to include withholding the specific topics addressed by the intervention from eligible patients until after they have enrolled and attended their scheduled appointment. We will obtain prospective agreement from patients for this alteration during the consent process. We also propose using a small number of unnecessary screening questions to obfuscate the specific purpose of the study at the time of screening. Once patients have completed their scheduled appointment, and before any outcomes are assessed in the post-visit survey, patients will learn about the information that was withheld from patients using the Deception Debrief Script (Attachment P). Patients will learn about the information that was withheld from them either from the RAs if they complete the post-visit survey by telephone, or at the beginning of the post-visit survey if they complete the survey online via Qualtrics. We are proposing this minimal alteration in consent procedures because discussing the specific topics addressed by the tool and intervention with eligible patients could prime patients in the control arm to discuss reproductive planning with their medical provider during their scheduled appointment. Since the occurrence and the quality of reproductive planning discussions between patients and providers is our primary outcome, we hope to minimize the extent to which we prime control arm patients to discuss these topics.

Withheld Information and Prospective Agreement: As detailed in the patient information statement (Attachment J) and during verbal consent processes (Attachment L), we will inform potentially eligible patients that this study is trying to improve the primary care that women Veterans receive and is evaluating a web-based decision tool designed for women Veterans. The purpose of the intervention will be described as helping women Veterans get the most out of their primary care visits and make informed health care decisions. We will inform patients that we are interested in studying whether the intervention affects the type and quality of discussions patients have with their providers and their decisions. We will state that we are choosing not to reveal the specific topics addressed by web-based tool until after enrolled patients have seen their medical provider so that we do not influence what they decide to discuss with their providers. Patients will be informed before they decide whether or not to enroll in the study that the specific purpose of the study and the specific topics addressed by the intervention will be revealed after they have seen their provider and before we ask them any questions about their medical appointment.

Added Screening Questions: We will screen patients on the inclusion and exclusion criteria detailed below in section 5.4. Screening questions may also be found in the patient survey instruments (Attachment Q) and in the patient screening and consent script (Attachment L). In addition to asking potentially eligible patients whether they would like information about pregnancy and birth control, we will also ask if they are interested in receiving information about other health-related topics, including sleep, healthy weight, pain, smoking cessation, and stress management. Including those additional, unnecessary screening questions will reduce the extent to which eligible participants are primed to discuss pregnancy and birth control with their providers and will help to maintain the obfuscation of the specific topics covered by the intervention until after they have received the intervention or seen their provider.

Analysis of Potential Risks to Patients: An alteration to consent procedures such as what we propose may pose additional risks to patients. Patients may feel discomfort once the full details of the study purpose are revealed to them and may decide they no longer wish to participate after the study purpose is revealed to them. We are taking the following measures to reduce the risks that our proposed alteration poses:

- The withholding of information about the study purpose will be made clear in the study information statement and by RAs doing screening, consent, and enrollment. Patients can choose whether or not to enroll in the study knowing that this information will not be revealed to them until after their scheduled appointment.
- We will provide as much information about the study as possible without revealing that our outcomes are related to reproductive planning. All information provided in the study information sheet and by RAs about the study will be accurate. No inaccurate or misleading information about the study will be provided to patients.
- The withheld information will be revealed to participants using the Deception Debrief Script (Attachment P) as soon as withholding the information is no longer necessary to the conduct of the study. This will be after they have attended their medical appointment and before the post-visit survey. Participants will be offered the opportunity to ask any questions they have and will be asked if they are comfortable continuing to participate in the study.
- Patients will be screened and included in the study only if they say they are interested in receiving information about pregnancy planning and/or birth control (see inclusion and exclusion criteria in section 5.4), which means the intervention is concordant with the patients' desires for information. This reduces the likelihood that enrolled patients will find the MyPath intervention or the purpose of the study to be intrusive or offensive.
- The additional, unnecessary screening questions are not of a sensitive nature, and patient answers to the additional screening questions will not be recorded or stored as part of study datasets.

5.4 Inclusion/Exclusion Criteria

Providers:

Inclusion Criteria:

- Primary Care Provider (MD, Nurse Practitioner, Physician Assistant) at a study site
- Designated as a Women's Health Provider [defined in VA directive 1330.01 as primary care providers who have demonstrated proficiency (e.g. pelvic exams and pap smears) in women's health and who have at least 10% of their panel comprised of women]
- Completed appointments with at least 30 unique female patients ages 18-44 in the past year at a study site. If a study site does not have enough providers who meet this

criterion and are willing to enroll in the study, the study team may reduce the minimum to 15 unique female patients ages 18-44 in the past year at a study site. (pulled from CDW)

Exclusion Criteria:

- Previous involvement as provider in MyPath pilot work (identified by PI/SC)
- Medical trainee (e.g., resident physician or medical student)
- Self-report that they have plans to leave VA, go on extended leave, retire, stop primary care practice, or change VA site in the 18 months following their enrollment

Patients:

Inclusion Criteria:

- Female (obtained via CDW)
- 18 – 44 years old (obtained via CDW)
- Has a scheduled VA medical appointment with an enrolled study provider and plans to attend the appointment at the time of enrollment (obtained via VSSC and/or CDW)
- Interested in receiving information or talking with their provider about pregnancy planning and/or birth control
- At least one valid telephone number available in medical record (obtained via CDW)

Exclusion Criteria:

- Medical record history of hysterectomy, bilateral oophorectomy, female sterilization, or diagnosed infertility for another reason
- Self-reported history of hysterectomy or bilateral oophorectomy
- Self-report of not having a uterus or ovaries (e.g. transgender women), which precludes the capacity to become pregnant
- [For VAPSHCS patients] Self-report of completing MyPath decision tool previously (e.g. during pilot study or Quality Improvement work).
- Unable to communicate in English
- Impaired decision making (by ICD code, from CDW)
- Currently pregnant
- Self-report that they have opted out of VA text messages, or that they are unable to receive text messages

Clinic Leaders:

Inclusion Criteria:

- Managerial role in a VA clinical setting where at least one enrolled provider practiced during study data collection

Exclusion Criteria:

- none

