Potentially vulnerable groups that may be included in our patient population because we are not specifically excluding them include employees or students; economically and/or educationally disadvantaged persons; and patients that identify as racial or ethnic minorities. It is unlikely that study eligible patients will be illiterate or have limited English language proficiency as these are requirements of military service enrollment. Pregnant women will be excluded from the study because the MyPath intervention is designed for non-pregnant women. Additional groups that will be excluded include women who are not capable of pregnancy (e.g., with known infertility for reasons such as hysterectomy or tubal sterilization), who are not interested in receiving information about birth control or planning for pregnancy, and women who are older than 44, as fertility and risk of pregnancy drops significantly over this age.

Minimizing Anticipated Risks

Risks to VA employees (providers and clinic leaders): The primary risk of the study to VA employees is the potential of disclosure of confidential or sensitive data. Although unlikely, employees may experience discomfort while completing self-report surveys or qualitative interviews. In addition, providers may perceive additional burden due to seeing patients who have used the MyPath tool. We anticipate this burden to be minimal, however, as no providers in our pilot study felt that that MyPath added significant burden and some providers felt that MyPath made counseling more efficient because patients were informed about their options. The following strategies will help minimize risks to employees:

- The Seattle Health Services Research & Development (HSR&D) Center of Innovation (COIN) has developed extensive security measures (discussed below in section 7.0) to minimize the risk of disclosure of confidential or sensitive data.
- Steps will be taken to minimize the risk of invasion of privacy. Employees will be sent a recruitment email, which will include the study information sheet. This email will invite employees who do not wish to be contacted further about the study to opt-out of further contact/recruitment efforts by responding to the email.
- When reached by telephone for recruitment, consent, and enrollment, study staff will discuss the voluntary nature of study participation with employees, emphasizing that their choice of whether to participate will not affect their employment or work environment.

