Because informative missingness would violate the covariate-dependent missing at random (CDMAR) assumption of the standard multiple imputation procedure, we will conduct sensitivity analyses in which we multiply impute missing data under plausible informative missing data mechanisms – in particular, lower contraceptive continuation rates among participants with missing values of this outcome, in one or both arms. In all analyses, we will check for departures from model assumptions.

Aims 1 and 2 - Outcome Analyses:

Intention to Treat: Primary analyses of treatment effects will be intent-to-treat, with participants analyzed in the groups to which they were originally assigned irrespective of whether or not they received the intervention. Therefore, participants who “cross-over” from their assigned study arm will be analyzed in their originally assigned group. Participants will be withdrawn/removed from the study and excluded from analysis after enrollment in either of these circumstances:

- Participants who do not attend their scheduled visit with the study provider after enrollment (and thus have an undefined outcome for patient-provider reproductive planning discussion).
- Participants who find out they are pregnant during their enrollment visit (and thus would have been ineligible had this been known prior to enrollment).

Secondary analysis will utilize causal inference methods (e.g., using instrumental variables) to estimate the treatment effect between participants who actually used the MyPath tool vs. those who did not (i.e., accounting for adherence).

Analytic Subgroups: Certain secondary outcomes will be analyzed only among a pre-defined cohort/subgroup of participants. Assignment to these groups is made at patient screening/enrollment (pre-intervention). Definitions of the full sample and analytic subgroups are as follows:

- **The full sample:** includes all individuals who are eligible for and enrolled in the study based on inclusion/exclusion criteria (capable of pregnancy with no prior history of hysterectomy, oophorectomy, sterilization, not currently pregnant, interested in receiving information about either pregnancy planning or birth control, and able to receive VA text messages).

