- **At risk of unintended pregnancy (UIP):** a subgroup of the full sample defined as having had sex with a man in the past 12 months who has not had a vasectomy and not currently seeking pregnancy. Outcomes related to contraception will be assessed in the subgroup at risk for UIP.
- **Considering pregnancy:** a subgroup of the full sample who are considering or ambivalent about pregnancy in the next few years. The exploratory preconception health behaviors outcomes will be assessed in this subgroup.

Description of the study populations: Provider, patient, and clinic leader participants will be described through summary statistics of demographic characteristics, and for providers, practice characteristics.

Aim 1 Primary Outcome: The analysis for our primary outcome of patient-provider discussion of reproductive planning with share decision making (SDM) will be assessed post-visit in **the full sample**. For our Aim 1 primary outcome analysis, we will use a mixed effects logistic regression model to test whether the odds of occurrence of reproductive planning with SDM is significantly different in the intervention versus control arm post-visit. In addition to estimating the odds ratio, we will also estimate the difference in predicted probabilities between the intervention and control group.

Covariates to be included in adjustment models are as follows:

- Study site (categorical)
- Clinic practice-type (binary) – Women’s Clinic Y/N
- Visit Type (virtual/telephone vs. in-person)
- Patient Age (categorical)
- Patient Race/ethnicity (categorical)
- Patient Household Income (categorical)
- Patient Marital Status (categorical)
- Patient Parity (categorical)
- Mental Health Diagnosis (one or more, binary)
- Medical Comorbidity (one or more, binary)

Aim 1 Secondary Outcomes: Secondary outcomes for Aim 1 will be assessed post-visit.

Secondary outcomes assessed **in the full sample** include provider-patient communication self-efficacy and reproductive planning knowledge. Secondary outcomes assessed **in the subgroup at risk of UIP** include contraceptive decisional conflict, values concordance, and contraceptive method decision. We will use a mixed effects logistic regression model to test whether these outcomes are different in the intervention versus control arm post-visit.

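### Sterilization is an exclusion only when it is in the medical record, so a sterilized woman whose record is silent can be enrolled and counted as at risk of unintended pregnancy

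*Combined protocol and SAP*

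**What the plan says.** Section 5.4 has three patient exclusions that bear on the capacity to conceive:

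- By record: "Medical record history of hysterectomy, bilateral oophorectomy, female sterilization, or diagnosed infertility for another reason".
- By self-report: "Self-reported history of hysterectomy or bilateral oophorectomy".
- By self-report of anatomy: "Self-report of not having a uterus or ovaries (e.g. transgender women), which precludes the capacity to become pregnant".

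Sterilization appears only in the first. The recruitment lists in Sections 5.1 and 5.2 are also screened on database or medical-record evidence.

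Two other places describe who is in the trial without limiting the source of evidence. Section 5.1 (Study Population) says that women unable to become pregnant are excluded, "with known infertility for reasons such as hysterectomy or tubal sterilization". Section 5.6 (Analytic Subgroups) defines the full sample as everyone eligible and enrolled under the criteria, and glosses this as "capable of pregnancy with no prior history of hysterectomy, oophorectomy, sterilization, not currently pregnant".

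Section 5.6 then defines the UIP group, within the full sample, as "having had sex with a man in the past 12 months who has not had a vasectomy and not currently seeking pregnancy". It adds: "Outcomes related to contraception will be assessed in the subgroup at risk for UIP". The outcomes analysed there are decisional conflict, values concordance and method decision after the visit, and continuous use, consistent use and unintended pregnancy at 3 and 6 months.

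**The concern.** The plan backs up the record with self-report for hysterectomy and oophorectomy, which makes sense only if the record can miss a procedure. It gives no reason why sterilization, named in the same record-based criterion, has no such backup. A procedure done outside VA is the obvious example, although the documents do not say how often that happens.

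A sterilized woman whose record is silent meets the listed criteria if she also meets the rest. If she has had sex in the past year with a man without a vasectomy and is not seeking pregnancy, she also meets the literal UIP definition. She cannot have an unintended pregnancy, and her contraceptive status is fixed. The main text does not say whether sterilization counts as continuous or consistent use, so her value on those outcomes, and on the goals-concordant measures built from them, is undefined. The group analysed could then differ from the group the report describes.

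**Working it through.** **Step 1: follow one woman through the text.** She was sterilized before enrolment and the record does not show it.

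| Stage | Rule | Does it remove her? |
|---|---|---|
| Recruitment lists (5.1, 5.2) | Database or record evidence | No |
| Record exclusion (5.4) | Needs a record entry | No |
| Self-report exclusion (5.4) | Hysterectomy, bilateral oophorectomy | No |
| Anatomy exclusion (5.4) | No uterus or ovaries | No |
| Interest criterion (5.4) | Pregnancy planning and/or birth control | Only if she has no interest |
| Removal after enrolment (5.6, 5.7) | Visit missed, or pregnancy found at the visit | No |
| UIP definition (5.6) | Partner vasectomy; seeking pregnancy | No, on her own sterilization |

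Only the descriptive statements in 5.1 and 5.6 would exclude her, and no listed step applies them to self-report.

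**Step 2: the plan's own figure.** The sample size concerns the primary outcome in the full sample. For 50% against 70%, two-sided 5% and 80% power, n = [1.960·√(2·0.6·0.4) + 0.842·√(0.25 + 0.21)]² / 0.20² = 93 per arm. Inflating for 30% non-use (1/0.7²), for clustering (reading the stated kappa of 0.01 as the clustering coefficient, 1 + 14·0.01 = 1.14) and for 5% attrition gives 2·93/0.49·1.14/0.95 = 455.5, so 456. The stated figure reproduces. It does not depend on this point, and the plan states no power for any UIP outcome.

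**Step 3: outcomes on which these women cannot respond.** Let f be their share of the UIP subgroup. The documents give no value, so 2%, 5% and 10% are assumptions. With the outcome variance held roughly constant, the absolute effect shrinks by (1−f). For an illustrative comparison with 80% power, the expected z is 1.960 + 0.842 = 2.802.

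- Women kept: power = Φ(2.802·(1−f) − 1.960). Effective sample = (1−f)².
- Women removed: the effect is restored and n falls to n(1−f), so power = Φ(2.802·√(1−f) − 1.960).

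| f | Effective sample lost if kept | Power if kept | Power if removed | Gain (points) |
|---|---|---|---|---|
| 2% | 4.0% | 78.4% | 79.2% | 0.8 |
| 5% | 9.8% | 75.9% | 78.0% | 2.1 |
| 10% | 19.0% | 71.3% | 75.7% | 4.4 |

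Removing enrolled women recovers only part of the drop from 80%, because their places in the sample are already spent.

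**Step 4: unintended pregnancy.** Here a share f has zero risk in both arms. Risks p₁ and p₀ become (1−f)p₁ and (1−f)p₀, so the risk ratio is still p₁/p₀. For a rare outcome the odds ratio from the planned logistic model is nearly the same. The risk difference scales by (1−f) and the variance by about (1−f), so z scales by (1−f)/√(1−f) = √(1−f). Removing the women leaves the same events in n(1−f) women, and z again scales by √(1−f). The loss is about f of the effective sample, and removing enrolled women recovers essentially none of it.

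**The case against.** The strongest reply is that the UIP group is defined inside the full sample, which Section 5.6 describes with the words "capable of pregnancy with no prior history of hysterectomy, oophorectomy, sterilization". On that reading the condition is inherited, and the vasectomy clause is there only because partner status is not covered upstream. A reader might otherwise infer that the plan deliberately counts sterilized women as at risk. The documents do not support that, since the stated intent is the opposite. What survives is operational: the full sample consists of those eligible and enrolled under the criteria, the parenthesis only summarises those criteria, and for this item the summary is not accurate.

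A reader might also infer that a woman who tells the research assistant she is sterilized is certainly enrolled. That goes too far. The screening script and survey instruments (Attachments L and Q) are not available and may ask the question. It remains true that no criterion or analysis rule in the main text would act on the answer.

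Two filters, the record check and the interest criterion, make a large share unlikely. The models for continuous and consistent use adjust for contraceptive use before the study, which may absorb some of the fixed-status variation. Both points stand, and they limit the size of the problem without closing the gap.

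**Conclusion.** The point holds as a small, correctable inconsistency. Sections 5.1 and 5.6 describe a sample without sterilized women, and the criteria in 5.4 do not secure it. The UIP subgroup inherits the gap.

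The likely effect is some loss of precision, dilution of the contraception outcomes and ambiguous coding. Its size rests on an unknown share. The figures for 2%, 5% and 10% are illustrations and assume that these women cannot respond on the outcome at all.

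Three stronger conclusions are tempting and are not supported:

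- **Bias between arms.** Arm is set by randomizing providers, and recruiters are blinded to providers' arms. Nothing suggests that sterilized women would enter one arm preferentially.
- **Every UIP outcome is pulled toward no difference.** Step 4 shows that this fails for the ratio estimate of unintended pregnancy.
- **The trial falls short of its stated power.** The only stated power is for the primary outcome, and no power is stated for the UIP outcomes.

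**What to change.** 1. Reconcile Sections 5.1, 5.4 and 5.6 on whether sterilization known only from self-report excludes a woman from the sample, from the UIP subgroup, or from both.
2. For any remaining enrolment, add sterilization to the self-report exclusion in 5.4.
3. Before unblinded analysis, define the UIP subgroup as also requiring no recorded or self-reported sterilization before enrolment. This is a characteristic fixed before the intervention, so it fits the plan's rule that subgroups are assigned at screening or enrolment, and it preserves the randomized comparison.

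The cost is one criterion, one line in the subgroup definition and a marginally smaller UIP subgroup. One more reproductive item at screening also carries a small priming risk, which matters because Section 5.3 deliberately masks the topic before the visit. The risk should be slight, since self-reported hysterectomy and oophorectomy are already criteria.
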